3.1 General Considerations

Two formal analyses (Stage 1 analysis and Stage 2 analysis) as well as an interim analysis are planned for the study.

The Stage 1 analysis for the overall population will be conducted after the last non-Japanese subject has completed the Week 53 visit or discontinued prematurely (this analysis will include all Japanese subjects who have completed Week 53). The Stage 2 analysis for long-term safety follow-up will be performed after all subjects have completed the study or discontinued prematurely. During the Stage 1 analysis, all the efficacy and safety data

Version 2.0

collected will be analyzed. Pairwise comparisons between individual tralokinumab treatment groups and combined placebo will be conducted. The primary analysis for which the study is powered will be completed in the Stage 1 analysis, and the analyses based on primary efficacy endpoint will be repeated for overall population (which includes all subjects enrolled into the study) at the end of the study as sensitivity analysis.

The interim analysis will be conducted after the last non-Japanese subject randomized into the study has completed the Week 39 visit or discontinued prematurely. All data available will be analyzed as part of the interim analysis. The details of the interim analysis will be specified in unblinding plan for interim analysis.

The overall type I error rate (two-sided) will be controlled at the 0.15 level using O'Brien-Fleming alpha spending function based on the actual person-years follow-up observed. For example, if the information fraction at the interim analysis is 88%, then the two-sided type I error rate will be 0.105 for the interim analysis and 0.128 for final analysis, respectively. The interim analysis will have minimal impact on the power of the study at the final analysis, which is estimated to be approximately 78%.

Three sets of analyses will be performed at Stage 1. They are: 1) analyses based on overall population; 2) analyses for Japan only subjects (n=45); and 3) analyses for non-Japanese subjects. The go/no-go decision will be based on stage 1 analysis for overall population.

In addition, for PMDA consultation, the same analyses for all Japan subjects (n=64) will be conducted when all Japan subjects complete week 53 follow-up or discontinue prematurely.

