2.3 Sample Size Considerations

Sample size calculations have been performed by simulations combined with normal approximation. Simulations assume the data follow exact Poisson distribution. Simulated data have been analyzed using Poisson regression without adjusting for overdispersion.

A total of 390 subjects will be randomized in a 1:1 ratio to one of 2 cohorts (Cohorts 1 or Cohort 2). Within each cohort, subjects will be randomized in a 2:1 ratio to receive SC tralokinumab (300 mg) or placebo. The primary analysis will be based on the ITT population.

Fifty-three subjects per treatment arm would be required to detect a 40% reduction in annual asthma exacerbation rate for each tralokinumab cohort compared to placebo assuming an annual exacerbation rate in placebo group of 1.2 with 80% power and a significance level of 0.1. Sample size was increased to 65 per treatment arm to accommodate overdispersion of 1.2. Recent data suggest that approximately half of asthmatic subjects may have a molecularly distinct subtype of asthma characterized by IL-13-driven inflammation; it is reasonable to hypothesize that these IL-13-positive subjects will have the optimal response to tralokinumab therapy. Therefore the sample size has been increased from 65 to 130 subjects per treatment arm to allow for a subanalysis to explore the relationship between the clinical response to tralokinumab and the presence of peripheral blood biomarkers associated with upregulation of IL-13 in the asthmatic lung. In the event that the clinical response is observed only in IL-13-positive subjects, this sample size retains adequate power to detect a difference in the asthma exacerbation rate comparing IL-13-positive tralokinumab treated subjects versus placebo. As presented below, the power to detect a 40% reduction in the exacerbation rate will depend upon the positive predictive value of the peripheral blood biomarker with respect to actual lung IL-13 expression (Table 1).

Table 1	Peripheral Blood Biomarker Positive Predictive Value
Table I	relipheral blood blomarker Positive Predictive value

Peripheral Blood Biomarker PPV	Two-sided alpha	Power (Individual Tralokinumab vs. Placebo)
100%	0.1	81.9%
90%	0.1	73.5%
80%	0.1	61.6%
75%	0.1	57.3%

IL-13 = interleukin-13; PPV = positive predictive value

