3.2.1 Intent-to-treat (ITT) Population

The intent-to-treat (ITT) population includes all subjects who are randomized into the study. Treatment arm will be assigned according to the initial randomization, regardless of whether subjects receive any investigational product or receive an investigational product different from that to which they were randomized.

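### Read literally, the Stage 1 rule for Japanese subjects selects on completing Week 53, which omits Japanese early discontinuers from the primary ITT analysis and conflicts with the SAP's own population definitions

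*SAP*

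**What the plan says.** SAP Section 3.1 sets the timing of Stage 1: it is "conducted after the last non-Japanese subject has completed the Week 53 visit or discontinued prematurely". A bracket then adds that "this analysis will include all Japanese subjects who have completed Week 53". The section gives Stage 1 its weight: "The primary analysis for which the study is powered will be completed in the Stage 1 analysis", and "The go/no-go decision will be based on stage 1 analysis for overall population". It plans three Stage 1 sets: overall, Japan only (n=45) and non-Japanese. A later analysis of all Japanese subjects (n=64) is to run "when all Japan subjects complete week 53 follow-up or discontinue prematurely".

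Other parts of the SAP bear on who should be counted:

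- Section 2.3: "The primary analysis will be based on the ITT population".
- Section 3.2.1: "The intent-to-treat (ITT) population includes all subjects who are randomized into the study".
- Section 3.2.3: the Safety population is everyone dosed who has safety data, with no completion condition.
- Section 3.5: the primary endpoint runs from first dose to Week 53 or the early discontinuation visit. Follow-up time enters the Poisson model as a log-days offset, and a separate adjustment is given for subjects who withdraw.
- Section 3.1, same paragraph as the bracket: the efficacy and safety data collected are all to be analysed at Stage 1.

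**The concern.** Completing Week 53 is a post-randomisation outcome. A programmer who follows the bracket would flag Japanese completers and leave out any Japanese subject who withdrew or died earlier, even one randomised more than a year before the cut-off. A non-Japanese subject with the same history stays in, because the ITT population carries no completion condition.

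Three things are at stake. First, the analysis called ITT would be ITT for one part of the trial and completers-only for the other. Second, if the Japan-only Stage 1 set follows the bracket, it contains no discontinuers, although Section 2.2.1 randomises Japanese subjects separately to obtain treatment balance; selecting on completion can undo that balance. Third, Sections 3.3 and 3.6.1.1 schedule Stage 1 tables of end-of-treatment status, fatal adverse events and adverse events leading to permanent discontinuation of study drug. These are the tables in which early leavers matter most.

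**Working it through.** **The passages side by side.** The ITT and Safety definitions impose no completion condition, the endpoint and offset accept partial follow-up, and Section 3.1 calls for all collected data at Stage 1. The bracket alone ties a subject's inclusion to completing Week 53. The later n=64 Japan analysis explicitly counts discontinuers.

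**Planning figures.** Section 2.3 gives a placebo rate of 1.2 per year, a 40% reduction (so 0.72), 80% power and alpha 0.1 (two-sided in its Table 1). The normal approximation gives n = (1.645 + 0.842)² × (1/1.2 + 1/0.72) / ln(0.6)² = 52.65, hence the stated 53 per arm. Multiplying by 1.2 for overdispersion gives 64, against the stated 65. The point does not depend on these figures; the rates are reused below.

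**Subjects omitted.** The Japanese discontinuation rate d is assumed, since the SAP gives none.

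| d (assumed) | If 45 counts completers: 45/(1−d) − 45 | If 45 counts everyone in the window: 45 × d |
|---|---|---|
| 5% | 2.4 | 2.3 |
| 10% | 5.0 | 4.5 |
| 15% | 7.9 | 6.8 |

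**Effect on the rate ratio.** All of the following is assumed: 130 subjects per group, of whom 45/3 = 15 are Japanese; true ratio 0.60 in completers; discontinuers followed for half a year at k times the completers' rate; the same dropout pattern in Japanese and non-Japanese subjects. An arm's rate with discontinuers kept is λ × [(1−d) + 0.5dk] / [(1−d) + 0.5d]; among completers it is λ.

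| Dropout active / placebo | k active / placebo | Japan-only: kept → omitted | Overall: kept → Japanese discontinuers omitted |
|---|---|---|---|
| 10% / 10% | 2 / 2 | 0.600 → 0.600 | 0.600 → 0.600 |
| 20% / 10% | 2 / 2 | 0.633 → 0.600 | 0.633 → 0.630 |
| 20% / 10% | 3 / 1 | 0.733 → 0.600 | 0.733 → 0.720 |
| 10% / 20% | 1 / 3 | 0.491 → 0.600 | 0.491 → 0.500 |

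Row 2, Japan-only: active 0.72 × (0.8 + 0.2)/(0.8 + 0.1) = 0.800; placebo 1.2 × (0.9 + 0.1)/(0.9 + 0.05) = 1.263; ratio 0.633.

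A milder case, with 5% active and 15% placebo dropout and k = 2 in both, gives a Japan-only ratio of 0.60 × 1.026/1.081 = 0.569 against 0.60 in completers.

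The largest overall shift here is 0.7333 − 0.7195 = 0.014. The direction depends on which arm loses more high-rate subjects.

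**The case against.** The strongest reply is that the bracket is not an exclusion rule. The word *only* is not there. The wording about non-Japanese subjects is a timing trigger, so the contrast is not between two inclusion criteria. After a trigger that ignores Japan, the bracket can be read as reassurance that Japanese data are not left out. Section 2.2.2 describes both stages in terms of completion without mentioning discontinuation, so the SAP uses completion as shorthand elsewhere. The sentence on analysing all collected data supports the wider reading.

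Much of this stands. It shows that intent to exclude is not established. It does not remove the conflict: the bracket is the most specific statement of which Japanese subjects enter Stage 1, and it can be programmed as written.

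It is also fair to say that nothing is lost for good. The primary-endpoint analyses are repeated on all enrolled subjects at the end of the study, the n=64 analysis includes Japanese discontinuers, and the main safety tables are repeated at Stage 2. All of these come after the go/no-go decision.

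Leaving out Japanese subjects still in follow-up at the cut-off is an ordinary administrative cut-off and is not criticised here.

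**Conclusion.** The point holds as a conflict within the SAP that should be resolved before unblinding. Followed literally, the bracket conditions the primary analysis on a post-randomisation outcome for Japanese subjects. If n=45 counts completers, about 2 to 8 subjects are omitted at assumed discontinuation of 5% to 15%. The overall ratio, on which the go/no-go rests, probably moves little: at most 0.014 in the assumed scenarios, and not at all when dropout and rates are alike across arms. The Japan-only ratio could move considerably more under differential dropout. These sizes are illustrations, because the SAP gives no dropout figures.

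A reader might infer three stronger things that the document does not support:

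- **That the 45 are all completers.** The SAP never says how 45 was counted.
- **That Japanese deaths and withdrawals cannot appear in any Stage 1 table.** This is true only on the strictest reading, against the sentence on all collected data.
- **That the alpha spending fails because the interim may hold subjects whom Stage 1 drops.** Section 3.1 does say "All data available will be analyzed as part of the interim analysis", but spending follows observed person-years, interim details are left to a separate unblinding plan, and no type I error effect has been shown.

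**What to change.** Replace the bracket in Section 3.1 with two rules.

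- **Stage 1 efficacy, overall and Japan-only:** include every randomised Japanese subject whose scheduled Week 53 date falls on or before the data cut-off, whether that subject completed Week 53 or discontinued prematurely. This depends on the randomisation date and not on outcome, and it keeps subjects still in follow-up out. Merely adding discontinuers to the present wording would not do: a recently randomised subject could then enter only by discontinuing, which over-represents discontinuers among late enrollees.
- **Stage 1 safety:** include all data to the cut-off from every dosed Japanese subject, in line with Section 3.2.3. The scheduled-date rule should not be used here, because it would hide an early death or withdrawal among the later enrollees (64 − 45 = 19 subjects lie outside the stated set).

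Restate n=45 if it counted completers only. The interim analysis needs no restriction on this account. The cost is two sentences and a population flag, with Japanese denominators that may differ between efficacy and safety tables. No planned sample size changes.

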3.2 Subject Populations

Four populations have been defined in this study, the Intention-to-Treat (ITT) Population, the Per-Protocol (PP) Population, the Safety Population, and the Evaluable Population for PK.

3.2.1 Intent-to-treat (ITT) Population

The intent-to-treat (ITT) population includes all subjects who are randomized into the study. Treatment arm will be assigned according to the initial randomization, regardless of whether subjects receive any investigational product or receive an investigational product different from that to which they were randomized.

3.2.2 Per-Protocol (PP) Population

The per protocol (PP) population includes all subjects who have no major protocol violations, complete the treatment period, and have received at least 80% of the intended doses of investigational product during the treatment period. Major protocol violations include:

- Did not fulfill major eligibility criteria (which will be defined prior to the database lock)
- Developed withdrawal criteria but continued
- Received incorrect investigational treatment/dose

Version 2.0

Treatment classification in PP Population will be on 'as-treated' basis.

3.2.3 Safety Population

The safety population includes all subjects who receive any investigational product and have safety data available. The safety analyses will be presented on an 'as-treated' basis.

3.2.4 Evaluable Population for PK

The evaluable population for PK includes all subjects who receive at least one dose of investigational product and have at least one detectable PK sample. Treatment classification in PK Population will be on 'as-treated' basis.

3.3 Baseline Characteristics

Several summaries, which include Subject Population for Evaluation, Number of Subject Randomized by Site, and Status of Randomized Subjects, will be provided to describe the study population. These summaries will aid in interpretation of the assessment of the primary, secondary and exploratory objectives and provide an overview of study conduct.

The summary of the number of subjects randomized by site will be sorted by site number and will contain the primary investigator's name/location.

The summary of randomized subject status at end of study will include an enumeration of the number of subjects who completed the study and the number who did not complete the study due to the following reasons: death, lost to follow-up, withdrawal of consent, and other.

The summary of randomized subject status at end of treatment will include the number of subjects who completed the protocol-defined end of treatment and the number who did not complete due to the following reasons: adverse event, death, lost to follow-up, withdrawal of consent, and other.

All the baseline characteristics (demographics, baseline disease characteristics, medical history and Asthma history) will be summarized by treatment group. In addition demographics and baseline disease characteristics will be summarized by cohort and by treatment group.

The following demographic characteristics will be summarized: age in years, gender, race, ethnicity, weight, height, and Body Mass Index (BMI). BMI is calculated as follows:

```
BMI = weight (kg) / [height (m)]^2
```

Version 2.0

The summary of baseline disease characteristics will include descriptive statistics for asthma history, chronic OCS use (presence versus absence), whole blood eosinophil count, atopic asthma status (atopic vs. non-atopic) (Atopy is defined by the presence of elevated IgE specific to any one common aeroallergen on the region-specific ImmunoCap panel tested at baseline), Th2 status identified by serum total IgE and blood eosinophils (Th2-high: IgE >100 IU/mL and blood eosinophils $\geq 0.14 \times 10^{9}$ /L) (Corren et al., 2011), serum periostin level, spirometry [pre- and post-bronchodilator FEV₁ and FEV₁ % predicted, FEV₁ reversibility, forced expiratory volume in 6 seconds (FEV₆) and FEV₆ % predicted, FVC, FVC % predicted, FEV1/FVC ratio and inspiratory capacity (IC)], and patient reported outcomes [Asthma Control Questionnaire (6-item version; ACQ-6) score, Asthma Quality of Life Questionnaire Standardized Version (AQLQ(S)), Assessing Symptoms of Moderate-to-severe Asthma (ASMA) Diary, WPAI-Asthma, and EQ-5D] by treatment group.

Prior and concomitant medications will be coded using the latest available version of AstraZeneca Drug Dictionary (AZ DD). All prior and concomitant medications (including those for Asthma indication) will be presented in a data listing.

The compliance with fluticasone/salmeterol maintenance therapy categorized as subjects with \geq 80% self-reported compliance rate and subjects with < 80% self-reported compliance rate as well as the number and percent of subjects who change their background asthma controller medications post randomization to Week 53 (Stage 1 analysis) and between week 53 and end of study (Stage 2 analysis) will be summarized by treatment group.

Summary	Population	Analysis
Study Populations for Evaluation		Stage 1
Number of Subjects Randomized by Site	ITT	Stage 1
Status of Randomized Subjects at End of Study	ITT	Stage 2
Status of Randomized Subjects at End of Treatment	ITT	Stage 1
Demographics	ITT	Stage 1
Baseline Disease Characteristics	ITT	Stage 1
Summary of Medical History	ITT	Stage 1
Summary of Asthma History	ITT	Stage 1

Compliance with Fluticasone / Salmeterol Maintenance Therapy	ITT	Stage 1
Number of Subjects with Change of Background Asthma Controller Medications Post Randomization	ITT	Stage 1 / Stage 2

3.4 Study Drug Exposure

The following summary will be provided:

Summary	Population	Analysis
Number of Study Drug Doses	Safety	Stage 1
Total Amount of Study Drug Exposure in mg	Safety	Stage 1
Total Amount of Study Drug Exposure by Dose in mg/kg	Safety	Stage 1

The summary of study drug exposure will include descriptive statistics for number of study drug doses and total amount of study drug (in both mg and mg/kg) administered to each subject as well as for dose intensity. The total amount of study drug (in mg and mg/kg) administered to the subject is defined as:

Total actual volume administered (ml) \times drug concentration (mg/ml) and

Total actual volume administered (ml) \times drug concentration (mg/ml) /weight.

For this trial, the drug concentration is 150 mg/ml.

3.5 Summaries to Support the Primary Objective

The primary objective of this study is to evaluate the effect of two SC treatment regimens of 300 mg tralokinumab compared with combined placebo by assessing the asthma exacerbation rate over 52 weeks in adults with uncontrolled, severe asthma requiring high-dose ICS and LABA with or without additional controller medications. An asthma exacerbation is defined as a progressive increase of asthma symptoms (cough, wheeze, chest tightness, and/or shortness of breath) that does not resolve after the initiation of rescue medications and remains troublesome for the subject resulting in either 1) use of systemic corticosteroids (tablets, suspension or injection) or increase of a stable systemic maintenance dose for a duration of at least 3 consecutive days as prescribed or administered by the investigator or

healthcare provider; or 2) subject initiation of systemic corticosteroids for a duration of at least 3 consecutive days as outlined in the Asthma Action Plan provided to the subject by the investigator on Day 1 An asthma exacerbation event will be considered resolved 7 days after the last dose of OCS is administered (10 days after administration of an injectable corticosteroid). Courses of corticosteroids initiated after this time period would be considered a separate new asthma exacerbation.

Asthma exacerbation severity will be classified as follows:

- Moderate: Worsening symptoms requiring systemic corticosteroids for at least 3 consecutive days.
- Severe: Worsening symptoms requiring systemic corticosteroids and requiring urgent care evaluation and/or hospital admission.

Please note that a single depo-injectable dose of corticosteroid will be considered the equivalent to a 3-day course of systemic corticosteroids

The primary endpoint will be the annual rate of asthma exacerbations experienced by subjects after their first dose of investigational product up to their week 53 / Early Discontinuation visit.

The crude asthma exacerbation rate will be estimated as a weighted mean (total number of exacerbations for the treatment group divided by the total duration of person follow-up) per the joint guidelines recommended by the ATS/ERS. The primary endpoint analysis will be conducted based on the ITT population using a Poisson regression model adjusted for overdispersion (Pearson Chi-Square correction) with treatment group, age, gender (male vs female), number of asthma exacerbations in the past year ($2 \text{ vs} > 2 \text{ but} \le 6 \text{ exacerbations}$), atopic asthma status (atopic vs. non-atopic), chronic OCS use (presence versus absence), and geographical region (United States/Canada/Western Europe, Eastern Europe, Asia, rest of world) as covariates and the log of number of days in the study as offset. Exacerbation rates, 85% CIs, rate ratios, 2-sided p-values will be provided based on the Poisson regression model. The primary endpoint will also be analyzed using a negative binomial regression model to assess the robustness with regard to the distributional assumptions. Pairwise comparisons between individual tralokinumab treatment group and combined placebo from Cohorts 1 and 2 will be conducted. Comparison between tralokinumab and placebo from the same cohort will be conducted as secondary analyses. Analysis based on the PP population will be performed as a sensitivity analysis.

The primary endpoint will also be analyzed using Cochran-Mantel-Haenszel row Mean Score Test. For analyses based on ITT Population, the adjusted number of exacerbations for subjects who withdraw from the study will be calculated using the following equation: [recorded number of exacerbations] / [number of days in the study] × 365.25.

Severe asthma exacerbations are of interest. The Analyses mentioned above will be conducted specifically for severe asthma exacerbations as well.

In addition, asthma exacerbations and severe asthma exacerbations between week 53 and end of the study, and asthma exacerbations and severe asthma exacerbations through the end of the study will also be summarized. Time to first exacerbation and time to first severe exacerbation will be analyzed as a supportive efficacy analysis to the primary objective. A Cox proportional hazard model will be fitted to data.

The number and proportion of subjects with different number of asthma exacerbations and severe asthma exacerbations (0, 1, 2, 3, and > 3) will be summarized by treatment group.

The following subgroups constitute subgroup populations of interest:

- 1) Subjects with percentage of predicted FEV1 at baseline $\leq 60\%$, and $\leq 80\%$;
- 2) Subjects with baseline % FEV1 reversibility (>= 12% and < 12%);
- Subjects with pre-bronchodilator FEV1 improvement at Week 5 and Week 13 (defined as percent change from baseline ≥ 10%) from tralokinumab group;
- 4) Subjects grouped by number of asthma exacerbations in the past year (2 vs > 2 but \leq 6 exacerbations);
- 5) Subject grouped by chronic OCS use (presence vs absence);
- 6) Subjects grouped by Th2 status (Th2-high: IgE >100 IU/mL and blood eosinophils $\geq 0.14 \times 10^{9}$ /L, and Th2-low);
- 7) Subjects grouped by atopic asthma status (atopic vs. non-atopic);
- 8) Subjects grouped by baseline serum periostin level (>= median or < median; ; >= 25^{th} percentile vs < 25^{th} percentile; >= 75^{th} percentile vs < 75^{th} percentile);
- 9) Subjects grouped by baseline peripheral blood eosinophil count (< 150 Cells/UL vs >= 150; < 300 Cells/UL vs >= 300).

The analyses described above except for comparisons between tralokinumab and placebo from the same cohort and for analyses for severe asthma exacerbations will be conducted for these subgroup populations.

For graphic presentation, cumulative number of asthma exacerbations and severe asthma exacerbations over time by treatment group, distribution of number of exacerbation by

Version 2.0

treatment group, forest plots of risk ratio (with 85% CI) for asthma exacerbations and severe asthma exacerbations for overall population and for each subgroup, and Kaplan-Meier curve of time to first asthma exacerbation and severe asthma exacerbation by treatment group will be created. Forest plots of risk ratio (with 85% CI) for asthma exacerbations and severe asthma exacerbations will also be created by baseline serum periostin level (< median, and >= Median; >= 25^{th} percentile vs < 25^{th} percentile; >= 75^{th} percentile vs < 75^{th} percentile) and by baseline peripheral blood eosinophil count (< 150 Cells/UL, 150 - < 300, and >= 300).

Summary	Population	Analysis
Summary of Asthma Exacerbation Rate through Week 53	ITT	Stage 1
Summary of Severe Asthma Exacerbation Rate through Week 53	ITT	Stage 1
Summary of Asthma Exacerbation Rate through Week 53	РР	Stage 1
Summary of Severe Asthma Exacerbation Rate through Week 53	РР	Stage 1
Summary of Asthma Exacerbation Rate between Week 53 and the End of Study	ITT	Stage 2
Summary of Severe Asthma Exacerbation Rate between Week 53 and the End of Study	ITT	Stage 2
Summary of Asthma Exacerbation Rate between Week 53 and the End of Study	РР	Stage 2
Summary of Severe Asthma Exacerbation Rate between Week 53 and the End of Study	РР	Stage 2
Summary of Asthma Exacerbation Rate through the End of Study	ITT	Stage 2
Summary of Severe Asthma Exacerbation Rate through the End of Study	ITT	Stage 2
Summary of Asthma Exacerbation Rate through the End of Study	РР	Stage 2
Summary of Severe Asthma Exacerbation Rate	РР	Stage 2

through the End of Study		
Time-to-First Asthma Exacerbation through Week 53	ITT	Stage 1
Time-to-First Severe Asthma Exacerbation through Week 53	ITT	Stage 1
Time-to-First Asthma Exacerbation through Week 53	РР	Stage 1
Time-to-First Severe Asthma Exacerbation through Week 53	РР	Stage 1
Time-to-First Asthma Exacerbation between Week 53 and the End of Study	ITT	Stage 2
Time-to-First Severe Asthma Exacerbation between Week 53 and the End of Study	ITT	Stage 2
Time-to-First Asthma Exacerbation between Week 53 and the End of Study	РР	Stage 2
Time-to-First Severe Asthma Exacerbation between Week 53 and the End of Study	РР	Stage 2
Time-to-First Asthma Exacerbation through the End of Study	ITT	Stage 2
Time-to-First Severe Asthma Exacerbation through the End of Study	ITT	Stage 2
Time-to-First Asthma Exacerbation through the End of Study	РР	Stage 2
Time-to-First Severe Asthma Exacerbation through the End of Study	РР	Stage 2
Number Subjects with at Least One Asthma Exacerbation through Week 53	ITT	Stage 1
Number Subjects with at Least One Severe Asthma Exacerbation through Week 53	ITT	Stage 1
Number Subjects with at Least One Asthma Exacerbation through Week 53	РР	Stage 1
Number Subjects with at Least One Severe Asthma	РР	Stage 1

Exacerbation through Week 53		
Number Subjects with at Least One Asthma Exacerbation between Week 53 and the End of Study	ITT	Stage 2
Number Subjects with at Least One Severe Asthma Exacerbation between Week 53 and the End of Study	ITT	Stage 2
Number Subjects with at Least One Asthma Exacerbation between Week 53 and the End of Study	РР	Stage 2
Number Subjects with at Least One Severe Asthma Exacerbation between Week 53 and the End of Study	РР	Stage 2
Number Subjects with at Least Asthma Exacerbation through the End of Study	ITT	Stage 2
Number Subjects with at Least Severe Asthma Exacerbation through the End of Study	ITT	Stage 2
Number Subjects with at Least Asthma Exacerbation through the End of Study	РР	Stage 2
Number Subjects with at Least Severe Asthma Exacerbation through the End of Study	РР	Stage 2
Number of Subjects with Different Number of Asthma Exacerbations through Week 53	ITT	Stage 1
Number of Subjects with Different Number of Severe Asthma Exacerbations through Week 53	ITT	Stage 1
Number of Subjects with Different Number of Asthma Exacerbations through Week 53	РР	Stage 1
Number of Subjects with Different Number of Severe Asthma Exacerbations through Week 53	РР	Stage 1

